9.5.5 Post-treatment Assessment of Menstruation

Time to first post-treatment menses will be summarized based on 28-day windows during the Follow-up Period: Study End Days 1 – 28, 29 – 56, 57 – 84, 85 – 112, 113 – 140, 141 – 168, and ≥ 169 . The number and percentage of subjects by who answered "Yes" to the question "Has the subject had a menstrual period since stopping study drug" with an onset date fall into the above time interval will be summarized by treatment group. The denominator is the number of subjects who answered the follow-up assessment of menstruation eCRF at each time interval.

9.5.6 Transvaginal Ultrasound

9.5.6.1 Ovarian Cysts

The presence of ovarian cysts will be noted at Baseline and each relevant post-baseline visit during the placebo-controlled and open-label Treatment Periods. Significant ovarian findings included complex ovarian cyst > 3.5 cm, simple ovarian cyst > 5 cm or endometriomas > 3 cm. The number and percentage of subjects with the pre-defined complex ovarian cysts and simple ovarian cysts will be summarized by treatment group at each relevant visit during the Treatment Period.

For each TAU/TVU assessment, information for significant ovarian findings from the cysts assessment may be available for more than one cyst at more than one ovary location (left and/or right). The subject with multiple cyst findings was counted once in the numerator and denominator when reporting the number and percentage of subjects in the relevant category of significant ovarian findings. A listing included all results across multiple cysts findings from multiple assessments (where available) from subjects who had significant ovarian findings.

9.5.6.2 Endometrial Thickness

The endometrial thickness at each relevant visit during the Treatment Period will be summarized with descriptive statistics. Additionally, analysis of change in endometrial thickness from Baseline to each relevant visit during the Treatment Period will be

performed. The mean change from Baseline each relevant visit during the 12-month placebo-controlled Treatment Period will be compared between each elagolix treatment group and placebo using one-way ANOVA with treatment as the main effect; no comparison will be conducted during the open-label Treatment period.

In addition, the number and percentage of subjects with endometrial thickness of < 8 mm, ≥ 8 mm and ≤ 12 mm, > 12 mm and ≤ 18 mm, and > 18 mm will be summarized by treatment group at each relevant visit during the Treatment Period. Each elagolix group will be compared to placebo using Fisher's exact test during the 12-month placebo-controlled Treatment Period; no comparison will be conducted during the open-label Treatment Period.

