Analysis details for Months 1-12 and Months 13-48 of the treatment period will be specified in the statistical analysis plan (SAP). No statistical tests will be performed following the 12-month placebo-controlled portion of the 48-month Treatment Period. Data from subjects randomized to the elagolix 200 mg BID alone will be summarized separately from subjects randomized to the elagolix 200 mg BID plus E2/NETA (1 mg/0.5 mg) QD arm. Unless otherwise specified, no statistical tests will be performed to evaluate potential differences between the two elagolix dose groups.

The mean change from baseline in key secondary endpoints will be analyzed using a mixed-effects model with repeated measures. Key secondary endpoints will be assessed at Month 3, Month 6 or Month 12. Other efficacy endpoints and analyses will be defined in the SAP.

For subjects randomized to placebo in the first 12 months of the treatment period, baseline will be re-set to the data collected the month prior to the first dose of elagolix in Months 13 - 48 of the treatment period. For subjects randomized to either one of the elagolix treatment groups, baseline for these subjects will refer to the baseline prior to the first dose of elagolix at the time of randomization.

Statistical Methods (Continued):

BMD Assessments:

The key BMD comparisons are in lumbar spine at Month 6 and Month 12. Secondary BMD endpoints include total hip and femoral neck. The elagolix 200 mg BID plus E2/NETA (1 mg/0.5 mg) QD dose will be compared to placebo at Months 6 and 12 and will be compared to elagolix 200 mg BID alone at Month 6 based on percent change from baseline. Percent change in BMD from baseline values, as well as Z-scores and T-scores at all time points will also be summarized. Analysis details will be provided in the SAP.

Safety Assessments:

All subjects who receive at least 1 dose of study medication will be included in the safety analyses. Hematology, chemistry (including lipid panel), urinalysis, vital signs, endometrial assessments and uterine bleeding variables will be summarized. Changes from Baseline to each Treatment Period visit during the first 12 months of treatment will be analyzed using an ANOVA or ANCOVA model as appropriate as specified in the SAP.

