8.1.7.1 General Considerations

All randomized subjects who took at least one dose of the study drug will be included in the safety analyses.

During the placebo-controlled treatment period (Months 1-12), baseline for all subjects will refer to the data obtained prior to Day 1. During the non-placebo controlled treatment period (Months 13-48), baselines will be defined as follows. For subjects randomized to elagolix or elagolix plus E2/NETA on Study Day 1, baseline for these subjects will refer to the baseline prior to the first dose of elagolix at the time of randomization. For subjects randomized to placebo in the first 12 months of the treatment period, their baseline will be reset to the data collected prior to reassignment at Month 13.

In general, for continuous variables, descriptive statistics (mean, standard deviation, median, minimum and maximum) will be summarized by treatment group. The treatment group differences in change and percent change from baseline will be analyzed using a one-way ANOVA with treatment as the main effect, or in some cases, one-way ANCOVA with treatment as the main effect, and baseline as a covariate. This will be detailed in the Statistical Analysis Plan.

Categorical data will be summarized with frequencies and percentages by treatment group. Fisher's exact test (or its generalization to $r \times c$ tables) will be used to analyze treatment group differences for qualitative categorical variables.

Unless specified otherwise, missing safety data will not be imputed.

Analysis details will be specified in the SAP.

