8.1.7.3 Analysis of Laboratory Data and Vital Signs

Changes from the baseline to each visit in continuous laboratory and vital sign parameters will be summarized by treatment group. Treatment group differences for changes from

baseline during the first 12 months of the treatment period will be analyzed using a one-way ANOVA with treatment as the main effect.

Laboratory values will be categorized as low, normal or high based on normal ranges of the central laboratory used in this study. Low or high laboratory values will be flagged in the data listings.

The number of subjects reaching potentially clinically significant levels will be summarized by treatment group. Criteria will be summarized by treatment group.

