9.0 Safety Analyses

9.1 General Considerations

Safety summaries will be provided separately using the Safety Analysis Set during the placebo-controlled Treatment Period, Safety Analysis Set during the open-label Treatment

Period, and All Elagolix plus E2/NETA Analysis Set as defined in Section 4.0. Unless otherwise specified, no statistical comparisons or tests will be performed on Safety Analysis Set during the open-label Treatment Period or the All Elagolix plus E2/NETA Analysis Set.

Unless otherwise specified, the baseline for the 12-month placebo-controlled Treatment Period will be the last non-missing value obtained prior to or on Study Day 1. The baseline during the open-label Treatment Period will be the last non-missing value obtained prior to or on the initiation day of elagolix (either elagolix alone or elagolix plus E2/NETA). The baseline for All Elagolix plus E2/NETA Analysis Set will be the last non-missing value obtained prior to or on the initiation day of elagolix plus E2/NETA.

All safety analyses will be based on observed data. Unless otherwise specified, missing data will not be imputed.

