9.3 Analysis of Laboratory Data

Data collected from central and local laboratories, including additional laboratory testing due to an SAE, will be used in all analyses, except for Baseline where SAE-related laboratory assessments on or before the first dose of study drug will be excluded. The clinical laboratory tests defined in the protocol operations manual (i.e., hematology and clinical chemistry) will be summarized.

Each laboratory variable will be summarized for all time points (starting with Baseline) with the number of non-missing observations, mean and standard deviation, median, minimum and maximum. Mean change from baseline to each applicable post-baseline visit will be summarized for selected laboratory variables, with the number of observations, baseline mean, and visit mean. The change from baseline mean, standard error, and 95% confidence interval will be presented for the mean change from baseline within each treatment group and difference between each elagolix group and placebo. Selected laboratory variables are lipid variables, liver variables (alkaline phosphatase, ALT, AST, bilirubin), hemoglobin, hematocrit, platelet count, and red blood cell (RBC) count. For lipid variables, in addition to low-density lipoprotein cholesterol (LDL-C), high-density lipoprotein cholesterol (HDL-C), total cholesterol, triglycerides (TG) and apolipoprotein A and B, the following ratios will be included: the ratio of total cholesterol to HDL-C, the ratio of LDL-C to HDL-C, the ratio of TG to HDL-C, and the ratio of non-HDL-C (calculated as total cholesterol minus HDL-C) to HDL-C.

Changes in selected laboratory parameters will be tabulated using shift tables by NCI CTC criteria and categorized as low, normal, or high based on the normal ranges of the laboratory used for each sample. A shift table from baseline either to the worse value (based on NCI CTC criteria) during treatment or to minimum and maximum value (based on normal range), will be created. A similar shift table will be provided to summarize shifts from baseline to the final post-baseline value.

Laboratory abnormalities meeting CTC criteria grade 3 or 4 will be summarized.

The number and percentage of subjects meeting the following sponsor-defined potentially clinically significant lipid values will be summarized at baseline and each relevant visit by treatment group in the appropriate Treatment Period:

- Total cholesterol: ≤ 300 , $> 300 - \leq 400$, $> 400 - \leq 500$, and > 500 mg/dL

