9.5.2.1 Bone Mineral Density during the Treatment Period

BMD

A summary of continuous BMD at each scheduled assessment will be provided during the appropriate Treatment Period. This summary will include the sample size, mean, SD, median, minimum, and maximum. This analysis will be repeated including subjects who switch machine manufacturer type (Lunar or Hologic), for subjects with scans only on Lunar machines, and for subjects with scans only on Hologic machines.

The analysis of percent change in BMD from baseline to each relevant visit during the Treatment Period will be based on an ANCOVA model with treatment as the main effect and baseline value of corresponding parameter as a covariate. Elagolix plus E2/NETA group will be compared to placebo at Months 6 and 12 and will be compared to the

elagolix alone group at Month 6 during the placebo-controlled Treatment Period. In addition, elagolix alone group will be compared to placebo at Months 6 and 12 during the placebo-controlled Treatment Period. This analysis will be repeated including subjects who switch machine manufacturer type (Lunar or Hologic), for subjects with scans only on Lunar machines, and for subjects with scans only on Hologic machines.

The number and percentage of subjects with percent change from Baseline to each scheduled assessment during the Treatment Period in mutually exclusive categories of BMD decrease: $\leq 0\%$, $> 0\% - \leq 1.5\%$, $> 1.5\% - \leq 3\%$, $> 3\% - \leq 4\%$, $> 4\% - \leq 5\%$, $> 5\% - < 8\%$, and $\geq 8\%$ will be summarized by treatment group. Elagolix plus E2/NETA group will be compared to placebo at Months 6 and 12 and will be compared to elagolix alone group at Month 6 during the placebo-controlled Treatment Period using chi-square tests. In addition, elagolix alone group will be compared to placebo at Months 6 and 12 during the placebo-controlled Treatment Period.

The analysis of percent change in BMD from Month 6 to Month 12 during the Treatment Period will be based on an ANCOVA model with treatment as the main effect and Month 6 BMD values of corresponding parameter as a covariate for subjects who have both Month 6 and Month 12 BMD values. Same analyses will be provided for percent change in BMD from Month 6 to Month 18 and Month 24. Each elagolix group will be compared to placebo.

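### Month 1–12 changes in endometrial thickness, laboratory values and vital signs are compared with placebo without the baseline value; the contrasts are valid but less precise than ANCOVA would make them

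*SAP*

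**What the plan says.** **Endometrial thickness.** SAP 9.5.6.2 has the mean change from baseline "compared between each elagolix treatment group and placebo using one-way ANOVA with treatment as the main effect" during the first 12 months. No covariate is named, and no confidence interval is promised for this comparison.

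**Laboratory data and vital signs.** Protocol 8.1.7.3 analyses changes over the first 12 months by "one-way ANOVA with treatment as the main effect". SAP 9.3 promises interval estimates instead: "95% confidence interval will be presented for the mean change from baseline within each treatment group and difference between each elagolix group and placebo". SAP 9.4 repeats this for vital signs. Neither SAP section names a model or a covariate.

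**What the plan allows and does elsewhere.** The protocol synopsis has safety changes "analyzed using an ANOVA or ANCOVA model as appropriate as specified in the SAP". Protocol 8.1.7.1 makes one-way ANOVA the general rule and, in some cases, ANCOVA "with treatment as the main effect, and baseline as a covariate". For percent change in bone mineral density, SAP 9.5.2.1 takes up that option: "ANCOVA model with treatment as the main effect and baseline value of corresponding parameter as a covariate". The pain scores, PROMIS Fatigue, EHP-30, EQ-5D-5L and WPAI change analyses also carry a baseline covariate (SAP 8.4 and 8.5). No reason is given for leaving it out of the three sets of measures above.

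**The baseline exists.** Under SAP 9.1, "the baseline for the 12-month placebo-controlled Treatment Period will be the last non-missing value obtained prior to or on Study Day 1". Protocol 5.3.1.1 takes baseline ultrasound findings from the Screening scan, and baseline laboratory values and vital signs from before dosing on Day 1.

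**The concern.** Comparing changes without a covariate fixes the slope of follow-up on baseline at 1. If the true slope is lower, subtracting the baseline adds noise, and any chance difference between arms at baseline passes into the estimate through regression to the mean. ANCOVA estimates the slope and avoids both.

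Thickness is where the loss could be largest. Protocol 5.3.1.1 asks for the Screening scan ideally on about Cycle Days 4–8, but gives the Month 12 scan a window of about 15 days either side and no cycle timing. A weak correlation between the two would not be surprising. By Appendix C, Month 12 is the only scheduled post-baseline scan in the placebo-controlled period, so repeated measures cannot recover the precision. Endometrial safety and lipid abnormalities are both listed in SAP Appendix B as events of special interest.

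At stake is the width of the intervals, and the sensitivity of the comparisons, for these safety measures in Months 1–12.

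**Working it through.** **1. The plan's own figure.** The only power statement (Protocol 8.2, SAP 2.4) concerns the co-primary responder endpoints. For NMPP, 54% vs 35% with 400 vs 200 women, the pooled rate is (216 + 70)/600 = 0.477. The null SE is sqrt(0.477 × 0.523 × 0.0075) = 0.0433, and the alternative SE is sqrt(0.54 × 0.46/400 + 0.35 × 0.65/200) = 0.0419. Power = Φ((0.19 − 1.96 × 0.0433)/0.0419) = 99.4%. For DYS (59% vs 23%) it exceeds 99.99%. Both agree with the stated figure of more than 90%. No precision target is given for the safety comparisons.

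**2. Inputs.** Arm sizes 400/100/200 are from SAP 2.3. The SDs and the baseline-to-follow-up correlation r are not in the documents, so r is varied.

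**3. Formulas, equal SDs s, common slope across arms.**
- Change-score variance per woman: 2s²(1 − r)
- ANCOVA variance per woman: s²(1 − r²)
- Variance ratio: (1 + r)/2; SE and interval-width ratio: sqrt((1 + r)/2)

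The 95% half-width in SD units is 1.96 × sqrt(variance per woman/s²) × sqrt(1/n₁ + 1/n₂). At r = 0.5 with 400 vs 200, the change score gives 1.96 × 1 × 0.0866 = 0.170, and ANCOVA gives 1.96 × 0.866 × 0.0866 = 0.147.

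| r | Variance ratio | Width ratio | Half-width 400 vs 200, change / ANCOVA | Half-width 100 vs 200, change / ANCOVA | 600 women by change score equal this many by ANCOVA |
|---|---|---|---|---|---|
| 0.3 | 0.65 | 0.81 | 0.201 / 0.162 | 0.284 / 0.229 | 390 |
| 0.5 | 0.75 | 0.87 | 0.170 / 0.147 | 0.240 / 0.208 | 450 |
| 0.7 | 0.85 | 0.92 | 0.131 / 0.121 | 0.186 / 0.171 | 510 |
| 0.9 | 0.95 | 0.975 | 0.076 / 0.074 | 0.107 / 0.105 | 570 |

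The half-widths assume that every randomised woman contributes; the width ratios do not depend on that. Simulation with 400/100/200 women and t-based intervals gave width ratios of 0.808, 0.867, 0.922 and 0.976. Since 2(1 − r) exceeds 1 when r is below 0.5, the change score is then noisier than the follow-up value alone.

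**4. Unequal SDs.** Let k be the follow-up SD divided by the baseline SD. The change-score variance minus the ANCOVA variance, in units of the baseline variance, is (1 + k² − 2rk) − k²(1 − r²) = (1 − rk)², which is never negative. It is zero only if the slope rk is exactly 1. For k from 0.5 to 1.5 and r from 0.1 to 0.9, the width ratio runs from 0.37 to 0.999.

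**5. Different slopes by arm.** Call the slopes b₁ (400 women) and b₀ (200 women). The common slope that minimises the variance of the contrast is (b₁ + 2b₀)/3, and a pairwise ANCOVA estimates (2b₁ + b₀)/3, which is |b₁ − b₀|/3 away. The change score's slope of 1 is 1 − (b₁ + 2b₀)/3 away. With both slopes between 0 and 1, the first distance never exceeds the second: if b₁ ≥ b₀ this needs 2b₁ + b₀ ≤ 3, and otherwise b₀ ≤ 1. ANCOVA is then asymptotically no less precise under 2:1 allocation.

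**The case against.** The planned analysis is valid and within the protocol. Protocol 8.1.7.1 makes ANOVA the default, the synopsis leaves the choice to the SAP, and ANCOVA is used for bone mineral density, the safety outcome with its own study objective. Ordinary chance imbalance is already covered by an unadjusted interval. All of that stands: this is a matter of efficiency, not of error.

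The size is also uncertain. No document gives a correlation, and equal SDs are doubtful when one arm is hormonally suppressed and another is cycling. That stands too, and is why a range is shown. The direction survives unequal SDs, and survives unequal slopes between 0 and 1 (steps 4 and 5).

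Mean change is not the only evidence. Thickness is also categorised and tested by Fisher's exact test, biopsies are tabulated, and lipids have threshold counts, shift tables and grade 3 or 4 summaries. By Month 12 the elagolix-alone arm has had six months of add-back, so its thickness contrast does not isolate elagolix alone. These points lower the priority, but none restores the precision lost in the mean comparison.

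Finally, the analysis may already have been run. SAP Version 2.0 is dated 08 May 2020, Protocol Amendment 7 describes all subjects as past Month 36, and the analysis is triggered once the last subject completes Month 12. This affects how the fix should be labelled.

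**Conclusion.** The point holds as a modest loss of precision in Months 1–12. With equal SDs, the unadjusted intervals are about 24% wider than ANCOVA's at r = 0.3 (1/0.806), 15.5% at r = 0.5 (1/0.866), 8.5% at r = 0.7 (1/0.922) and 2.6% at r = 0.9 (1/0.975). The loss may be material for thickness if its correlation is weak, and is modest for strongly correlated laboratory and vital-sign measures. Every one of these sizes rests on an assumed r.

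Three stronger readings are tempting and are not supported:
- A reader might infer that the safety comparisons are biased or invalid. Under randomisation they are neither.
- A reader might infer a specific large gain for thickness, such as an interval 23% narrower (r = 0.2, sqrt(0.60) = 0.77). The documents give no such correlation, and SAP 9.5.6.2 states no interval for that comparison.
- A reader might infer that conclusions on long-term safety are weakened. SAP 9.5.6.2 makes no thickness comparison in the open-label period, and SAP 9.1 excludes open-label safety comparisons unless otherwise specified.

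For laboratory data and vital signs, one-way ANOVA is the protocol's wording. The SAP's own gap is that it does not name its estimator.

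**What to change.** Low priority. In SAP 9.5.6.2, 9.3 and 9.4, estimate each between-arm difference in Months 1–12 by ANCOVA with treatment and the baseline value of the same measure, as SAP 9.5.2.1 does for bone mineral density. Report the adjusted difference with its 95% confidence interval, including for thickness. Keep the unadjusted within-group means as description. Align Protocol 8.1.7.3, which the synopsis and Protocol 8.1.7.1 already allow.

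If the Month 12 analysis has already been unblinded, leave the planned analysis in place and add the ANCOVA as a documented, labelled supplementary analysis.

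The cost is some wording and one covariate in existing code. No woman is lost, because a change score already requires a baseline value.

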9.5.6.3 Uterine Fibroids

The number and percentage of subjects with uterine fibroids present indicated by TVU will be summarized by treatment group at each relevant visit during the placebo-controlled and open-label Treatment Periods. The categories into which the number of fibroids are as follows: 0, 1, 2, 3, 4, 5, > 5, diffuse, and not evaluable. Subjects with multiple uterine fibroids present will be counted once in the numerator and denominator when reporting the number and percentage of subjects with uterine fibroids.

Listing of subjects with uterine fibroids will be presented.

9.5.7 Endometrial Biopsy

The number and percentage of subjects in each category of endometrial biopsy results will be summarized by treatment group at each relevant visit during the placebo-controlled and open-label Treatment Periods. If multiple assessments existed in a specific time window, all assessments will be displayed.

9.5.8 Pregnancy Results

Pregnancies and outcomes will be summarized by treatment group for the Treatment Period (placebo-controlled and open-label) and Follow-up Period. Subjects with

conception date by sponsor more than 30 days after the last dose of study drug will be included in the summaries for the Follow-up Period.

Listings will be prepared of all pregnancy test results for any subject who ever had a positive pregnancy test at any time point during the study.

Positive pregnancy test results (serum, urine, and both) and a listing of all positive pregnancy test results will be provided.

Pregnancy outcome will be summarized by treatment group. Additionally, a listing of pregnancy information will be provided. Pregnancy outcome includes:

- Number of pregnancies
- Live births
 - Pre-term (extremely pre-term: < 28 weeks; very pre-term: 28 - < 32 weeks; moderate to late preterm: 32 - < 37 weeks)
 - Term (37 - < 42 weeks)
 - Post-term (\geq 42 weeks)
- Spontaneous abortion (< 6, 6 - 13, > 13 weeks gestation)
- Termination of pregnancy
- Ectopic pregnancy
- Still birth
- Congenital anomaly
- Lost to follow-up
- Subjects refused to provide information
- Other
- Ongoing (pregnancy ongoing at end of study)
- Maternal exposure to Elagolix/Study drug (0, > 0 - 4, > 4 - 6, > 6 - 12, > 12 - 23, > 23 weeks)
- Embryo/Fetal exposure to Elagolix/Study drug assessed by the sponsor (0, > 0 - 4, > 4 - 6, > 6 - 12, > 12 weeks)

Annualized pregnancy rate during treatment will be reported by treatment group. The annualized pregnancy rate will be calculated as

$$\text{Annualized pregnancy rate} = (\text{number of pregnancies/days of exposure to treatment}) \times 365$$

In addition, listings of fetal/newborn, infant post-delivery assessments, and infant during 6 – 12 month follow-up assessment will be provided.

The above information will be summarized primarily based on data collected on the pregnancy case report form. Information not directly obtained from the case report form will use the following definitions.

Gestation day

Gestation Day 0 was calculated by subtracting the gestational age provided according to the first trimester ultrasound date from the first trimester ultrasound date. If no gestational age was provided, it will be imputed by subtracting 14 days from the midpoint between the subject's last negative pregnancy test date and the date of the positive pregnancy test.

Gestational age

Gestational age at delivery was calculated from gestation Day 0 to the date of delivery. Gestational age at abortion was calculated from gestation Day 0 to the date of abortion.

Conception date

Conception date by sponsor was calculated from the gestational age provided from the first trimester ultrasound, by adding 14 days to gestation Day 0. If no gestational age was provided, the conception date by sponsor was imputed as the midpoint between the subject's last negative pregnancy test date and the date of the positive pregnancy test.

Maternal exposure

Maternal exposure to study drug was calculated as the last dose date of study drug – the first dose date of study drug + 1.

Embryo/fetal exposure

Embryo/fetal exposure to study drug by sponsor was calculated from the conception date by site/sponsor to the date of maternal last dose of study drug.

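### Without an ultrasound age, SAP 9.5.8 dates conception at the midpoint between pregnancy tests with no detection lag, so embryo/fetal exposure and gestational age come out too short on average

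*SAP*

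**What the plan says.** SAP Section 9.5.8 derives three linked quantities for each pregnancy.

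- **Gestation Day 0.** With an ultrasound age, it is found by "subtracting the gestational age provided according to the first trimester ultrasound date from the first trimester ultrasound date". Without one, "it will be imputed by subtracting 14 days from the midpoint between" two test dates, namely the last negative and the positive.
- **Conception date.** With an ultrasound age: "Conception date by sponsor was calculated from the gestational age provided from the first trimester ultrasound, by adding 14 days to gestation Day 0". Without one, the rule changes: "the conception date by sponsor was imputed as the midpoint between" those same two test dates, with nothing subtracted.
- **Exposure of the embryo or fetus.** This runs from conception, as dated by the site or the sponsor, until the mother's final dose.

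Exposure is reported in the classes 0, >0–4, >4–6, >6–12 and >12 weeks. Gestational age at delivery or abortion is counted from gestation Day 0. A pregnancy whose sponsor conception date is more than 30 days after the last dose goes into the Follow-up summary. The section takes its data primarily from the pregnancy case report form and uses these definitions only for what the form does not supply directly.

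**The concern.** An interval that starts with a negative test and ends with a positive one contains the day on which the test turned positive. Conception came earlier, by however long a pregnancy takes to become detectable. The fallback treats the two dates as the same, which amounts to a detection lag of zero. The ultrasound branch does not depend on test conversion, so the same pregnancy would on average receive a later conception date under the fallback.

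A late conception date shortens embryo/fetal exposure, which is the non-conservative direction for a fetal safety summary. The same error makes gestational age at loss or delivery too young, and it can move a pregnancy across the 30-day line into the Follow-up summary. Protocol Section 3.2.2 reports two congenital malformations in clinical studies and calls the true relationship to elagolix unknown, so the exposure classes will be read with interest even though they are only descriptive.

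**Working it through.** **Inputs from the documents**

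- Pregnancy tests at each monthly visit (Protocol Section 5.1, Treatment Period).
- Months of 28 days and visits within ±5 days of the projected date (Protocol Section 5.3.1.1). Two consecutive scheduled tests can therefore be 28 − 10 = 18 to 28 + 10 = 38 days apart.
- Study drug paused while a positive urine test is confirmed (Protocol Section 5.2.4), so the last dose is taken here as the date of the positive test.
- The SAP rules set out above.

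**Assumptions not in the documents**

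- Detection lag L from conception to a detectable test: 8 to 14 days.
- The day the test turns positive is equally likely to be any day between the two tests.

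**Step 1: the SAP's own 14-day offset.** Let M be the midpoint between the tests. In the fallback, Day 0 = M − 14 and conception = M, so conception − Day 0 = 14 days. In the ultrasound branch, conception = Day 0 + 14. The two branches use the same offset, and the difference between them is 0 days.

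**Step 2: error of the fallback.** Let the gap between tests be I days, and let the test turn positive c days after the negative test. True conception is c − L; the rule says I/2. The error is I/2 − c + L. Since c averages I/2, the mean error is L for any test gap.

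Individual errors run from L − I/2 to L + I/2, so when L is below I/2 some exposures are overstated. With I = 28 and L = 8, the error runs from −6 to +22 days, and exposure is understated in (14 + 8)/28 = 79% of cases. At L = 14 it is understated in essentially all.

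**Step 3: exposure.** With the last dose on day I, the rule gives I/2 days. True exposure is spread evenly from L to I + L, with mean I/2 + L. The share above 4 weeks is (I + L − 28)/I, or 0 if that is negative.

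| Test gap I (days) | Rule gives (days) | True mean, L = 8 to 14 (days) | Share truly above 28 days, L = 8 to 14 |
|---|---|---|---|
| 18 | 9 | 17 to 23 | 0% to 4/18 = 22% |
| 28 | 14 | 22 to 28 | 8/28 = 29% to 14/28 = 50% |
| 38 | 19 | 27 to 33 | 18/38 = 47% to 24/38 = 63% |

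The rule places all three rows in the >0–4 week class. At a 38-day gap, 10/38 = 26% would exceed 4 weeks even with L = 0, so only the rest of that row is due to the lag.

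**Step 4: the zero class.** Take tests 28 days apart and a last dose 7 days before the midpoint. The rule gives no exposure. The lag-corrected midpoint gives 7 − (14 − L) = L − 7, which is 1 to 7 days.

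**Step 5: other derived fields.** Imputed gestational age is short by L on average. For an error of that size, a delivery at 38 weeks becomes 38 − 8/7 = 36.9 weeks at L = 8, or 38 − 14/7 = 36.0 weeks at L = 14. Both fall in the SAP's pre-term class (below 37 weeks). Similarly, a conception truly later than day 30 − L after the last dose (day 22 at L = 8, day 16 at L = 14), but not later than day 30, would be moved into the Follow-up summary.

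**The case against.** The strongest objection is that this is a residual rule. Protocol Sections 5.2.4 and 6.1.6 and Appendix C (note j) require a first-trimester ultrasound to date the pregnancy, the case report form takes precedence, and the exposure definition also admits a site conception date. No frequency for the fallback is given. It is plausible that missing ultrasound ages cluster in early losses, terminations and women lost to follow-up, but nothing in the documents shows it. The SAP also lists all pregnancy test results for any subject who ever tests positive, so a reader could bound each case by hand. All of this stands, and it limits the importance of the point.

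It is equally fair that the size rests on a lag the documents do not give. They fix neither 8 to 14 days nor any other value. The direction needs only a lag above zero.

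Some stronger readings are tempting and should not be drawn:

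- A reader might infer that the SAP defines conception in two ways about two weeks apart. It does not: Step 1 shows that the branches reconcile exactly. A two-week bias is only the case L = 14.
- A reader might infer that every imputed exposure is understated, or that the rule always gives 14 days. The understatement is an average, and 14 days requires tests exactly 28 days apart with the last dose on the positive-test date.
- A reader might infer that the table relates pregnancy outcome to exposure. The SAP lists outcomes and exposure classes as separate summaries by treatment group and specifies no cross-tabulation, model or test.

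**Conclusion.** The point holds and is minor. Where no ultrasound age exists, the SAP's midpoint dates test conversion and labels it conception. For any detection lag above zero, it dates conception late by that lag on average and shortens embryo/fetal exposure and gestational age equally.

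For L of 8 to 14 days, 28-day tests and a last dose at the positive test, 29% to 50% of such pregnancies would have more than 4 weeks of true exposure while being reported in the >0–4 week class. Across test gaps allowed by the visit window, the figure runs from 0% to 22% (18 days) up to 47% to 63% (38 days). These figures rest on the assumed lag, on even spread of the conversion day within the gap, and on the last-dose date. They describe only fallback pregnancies, which should be few. No efficacy result is affected.

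**What to change.** In SAP Section 9.5.8, where no ultrasound gestational age is available:

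1. Set the conception date to the test midpoint minus a pre-specified detection lag, with the source of the chosen value stated, and set gestation Day 0 to that date minus 14 days. The 14-day offset is kept.
2. Show exposure class, gestational-age class and the Follow-up assignment over a range of lags, for example 8 to 14 days.
3. List for each imputed pregnancy the longest possible exposure, counted from the last negative test minus the lag to the last dose.
4. State whether the site or the sponsor conception date takes priority, since the exposure definition names both.

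Item 3 is needed as well as item 1. With 28-day tests and a last dose at the positive test, the corrected estimate is 14 + L = 22 to 28 days, still in the >0–4 week class. The correction removes the average bias but does not show which pregnancies may have passed 4 weeks. The longest possible exposure, 28 + L = 36 to 42 days, falls in the >4–6 week class and makes that visible.

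The cost is one derivation, some SAP wording and an added listing column. Reported exposures in imputed cases become somewhat longer. No trial procedure changes.
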